not the PI believes the event to be related to the study. All other events, which are both serious and unanticipated, must be reported to the UC IRB within a time period as specified by current institutional guidelines after the PI learns of the event. Events which are serious, but anticipated, should be reported as part of the continuing review application. If any of these Serious Adverse Events requires a change to the protocol or consent form, the PI must make those changes promptly and submit the revised documents to the UC IRB. Important Adverse Events that are unanticipated must be reported to the UC IRB within a time period as specified by current institutional guidelines. If the Important Adverse Event requires changes to the protocol or consent form, the PI must make those changes promptly and submit the revised documents to the UC IRB. All other unanticipated Adverse Events or changes to the protocol and consent form must be reported to the UC IRB, within a time period as specified by current institutional guidelines.

IX. STATISTICAL CONSIDERATIONS

Study Overview

This pilot study is designed to assess the feasibility of giving neoadjuvant SBRT in resectable and/or borderline resectable pancreas cancer patients. The feasibility demonstration will establish the infrastructure for future randomized phase II clinical trials in a single or multi-center setting. Twenty patients with resectable and/or borderline resectable pancreas cancer, confirmed by multi-disciplinary radiologic review, will be enrolled and treated. The decision regarding whether this study demonstrates sufficient feasibility to support a phase II study testing novel regimens in this disease population will be based on three key considerations:

- The study can meet the accrual goal.
- The proposed preoperative SBRT will result in no more toxicity than has been established previously in the borderline resectable and locally advanced setting by evaluating the prevalence of grade 3+ toxicities and treatment delay rate (> 4 weeks).
- The completion rate of preoperative and operative therapy meets the goals.

Sample Size

A maximum of 20 patients will be enrolled if the trial completes accrual.

Accrual time

The anticipated monthly accrual rate is approximately 1-2 patients per month. The trial is expected to accrue in approximately 24 months.

Statistical Design for Primary Endpoints

Primary Endpoints

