- The primary endpoint is the rate of acute (within 3 months of treatment) G3+ gastrointestinal toxicities as assessed by CTCAE v4.0.

Study Design and Decision Rules

The purpose of this study is to demonstrate the feasibility of conducting a study assessing the proposed regimen. The sample size of twenty patients with confirmed resectable or borderline resectable pancreas cancer is selected based on financial and logistic considerations. However, we still propose decision rules based on testable hypotheses whenever possible. If, at the conclusion of the trial, none of the following stopping rules has been crossed, we will conclude that the proposed regimen and trial design warrants further phase II study for assessing SBRT followed by surgery in this disease population.

Accrual stopping rules

If, 4 months following the date IRB approval is obtained, no patients have been accrued, we will conclude the study does not demonstrate sufficient feasibility. Thereafter, the accrual rate will be monitored bi-monthly. If at any evaluation time point, the accrual rate is less than 0.5 per month, we will conclude the study does not demonstrate sufficient feasibility.

Toxicity Stopping Rules

The toxicity feasibility stopping rules are specified as the following:

- The toxicity rate is defined as the proportion of treated patients with resectable and/or borderline resectable pancreas cancer who experience at least one grade 3+ adverse event, and is considered at least possibly related to the preoperative treatment (i.e. an adverse event with attribute specified as “possibly,” “probably,” or “definitely” related to SBRT). The toxicity rate will be evaluated when the first 10, the first 15 and then 20 patients are enrolled and the toxicity data are available.
 - When toxicity data are available on the first 10 evaluable patients, if the toxicity rate is greater than 0.54 (> 5 patients experienced defined AEs), we will conclude the study does not demonstrate sufficient feasibility. Otherwise, continue accrual.
 - When toxicity data are available on the first 15 evaluable patients, if the toxicity rate is greater than 0.46 (> 6 patients experience defined AEs), we will conclude the study does not demonstrate sufficient feasibility. Otherwise, continue accrual.

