 - When toxicity data are available on all 20 evaluable patients, if the toxicity rate is greater than 0.42 (>8 patients experience defined AEs), we will conclude the study does not demonstrate sufficient feasibility.
 - This decision rule based on a sample size of 20 patients will have more than 80% chance to conclude the study does not demonstrate sufficient feasibility if the toxicity rate is $\geq 50\%$ and only have less than 17% chance to conclude the study does not demonstrate sufficient feasibility if the toxicity rate is $\leq 30\%$.
 - If 4 or more patients in the first 10, or after 10 patients, 40% or more treated patients experience treatment delay (> 4 weeks), we will conclude the study does not demonstrate sufficient feasibility.

Completion of Therapy Stopping Rules

The completion of therapy stopping rules are specified as the following:

- If at least 6 patients among 20 evaluable patients complete all preoperative and operative therapy including R0 or R1 resection, we will conclude the study warrants further phase II study, provided that none of the other feasibility stopping rules are crossed at any time.
- If 5 or less than 5 patients among 20 evaluable patients complete all preoperative and operative therapy we will conclude that the study does not demonstrate sufficient feasibility.
 - This decision rule based on a sample size of 20 patients will have more than 80% chance to conclude the study does not demonstrate sufficient feasibility if the R0/R1 resection rate is $\leq 20\%$ and only have less than 13% chance to conclude the study does not demonstrate sufficient feasibility if the R0/R1 resection rate is $\geq 40\%$.

Analysis Plan

All acute AE (within 3 months after treatment) and the maximum grade for each type of adverse events (including all adverse events and those that are possibly, probably or definitely related to study treatments) will be recorded for each patient. The frequency tables will be reviewed to determine the patterns. Point estimate and confidence interval will be reported for binary endpoints.

Supplementary Analysis Plans (Secondary Endpoints)

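### Each toxicity boundary is applied only once data are in on the whole group of 10, 15 or 20, with no stated pause; acting when the count is reached keeps the same crossing probabilities and stops a toxic regimen sooner

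*Combined protocol and SAP*

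**What the plan says.** Section IX, Toxicity Stopping Rules, counts patients with at least one grade 3+ adverse event at least possibly related to SBRT. The rate is "evaluated when the first 10, the first 15 and then 20 patients are enrolled and the toxicity data are available". The three boundaries are:

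- first 10 evaluable: "if the toxicity rate is greater than 0.54 (> 5 patients experienced defined AEs", so 6 or more;
- first 15 evaluable: "if the toxicity rate is greater than 0.46 (> 6 patients experience defined AEs", so 7 or more;
- all 20 evaluable: "if the toxicity rate is greater than 0.42 (>8 patients experience defined AEs", so 9 or more.

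If an interim boundary is not crossed, accrual continues. The rule does not define when toxicity data count as available, does not say whether accrual pauses while they mature, and does not provide for action before a look if the count is already reached. The plan says that this rule "will have more than 80% chance to conclude the study does not demonstrate sufficient feasibility" at a toxicity rate of 50% or more and will "only have less than 17% chance to conclude the study does not demonstrate sufficient feasibility" at 30% or less.

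On timing, Accrual time (Section IX) says: "The anticipated monthly accrual rate is approximately 1-2 patients per month". The same paragraph expects accrual to take about 24 months. The Analysis Plan sets the acute window: "All acute AE (within 3 months after treatment". The synopsis gives SBRT over 15 days. Safety Stopping Rules (Section IX) allow suspension at any time, but the only numeric trigger there is the rate of treatment-related deaths.

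**The concern.** A sixth affected patient among the first 10 settles the outcome of the first look, because later follow-up of the other patients can only add to the count. As written, nothing follows until data are available on the whole group. Patients may keep enrolling meanwhile, and with a cap of 20 the overrun after the look at 15 can use up most of the remaining places. At stake is how many patients enter a regimen that has already failed the trial's own rule. The safety rule does not close this gap, since non-fatal grade 3+ events have no running trigger.

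**Working it through.** **Inputs.** Boundaries 6/10, 7/15, 9/20 and cap of 20 (Section IX). Accrual 1 to 2 per month, or 20/24 = 0.83 per month from the 24-month figure. Lag: 15 days plus 3 months, about 3.5 months from SBRT start. The lag is an assumption, because the rule itself gives no window; it also takes SBRT to start at enrolment. Lags of 1.5 to 5 months are shown as a range.

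**1. The plan's own figures.** With X(n) the number affected among the first n and p the true rate:

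- Look 1: P(X(10) ≥ 6).
- Look 2: P(X(10) ≤ 5 and X(15) ≥ 7), the sum over k = 2 to 5 of P(X(10) = k) × P(at least 7 − k of the next 5).
- Look 3: P(X(10) ≤ 5, X(15) ≤ 6 and X(20) ≥ 9).

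| True rate | Look 1 | Look 2 | Look 3 | Total | Plan |
|---|---|---|---|---|---|
| 30% | 0.0473 | 0.0900 | 0.0299 | 0.1672 | below 17% |
| 50% | 0.3770 | 0.3258 | 0.0917 | 0.7944 | above 80% |

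The first figure is met. The second falls marginally short, at 79.4%.

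**2. Enrolment when the look at 15 is complete, without a pause.** Enrolled = min(20, 15 + whole part of rate × lag).

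| Lag (months) | 1 per month | 2 per month |
|---|---|---|
| 1.5 | 15 + 1 = 16 | 15 + 3 = 18 |
| 2 | 15 + 2 = 17 | 15 + 4 = 19 |
| 3.5 | 15 + 3 = 18 | 15 + 7 = 22, capped at 20 |
| 5 | 15 + 5 = 20 | 15 + 10 = 25, capped at 20 |

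At 0.83 per month and 3.5 months, 0.83 × 3.5 = 2.92, giving 17. With Poisson arrivals and a 3.5-month lag the means are 18.3 (1 per month), 19.7 (2 per month) and 17.8 (0.83 per month). At the look at 10, 13 to 17 are enrolled at 1 to 2 per month.

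**3. Acting when the count is reached.** The number affected among a fixed group never falls once events are confirmed. So the first 10 reach 6 at some moment if and only if they show 6 or more at the look; the same holds for 7 of 15 and 9 of 20. The two procedures cross in exactly the same trials. A patient-by-patient recursion gives the same totals, 0.1672 and 0.7944.

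The counts must stay tied to their groups. Stopping at any 6 events among 20 would cross with P(X(20) ≥ 6) = 58.4% at a 30% rate, against 16.7%.

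**4. Effect on enrolment.** Simulation of 100,000 trials per setting: Poisson arrivals, no pause, event times uniform over a 3.5-month lag (assumption). Mean enrolled, looks as written → running count:

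| True rate | Accrual per month | All trials | Trials that stop |
|---|---|---|---|
| 50% | 0.83 | 16.63 → 14.76 (−1.87) | 15.76 → 13.40 (−2.36) |
| 50% | 1 | 16.98 → 14.98 (−2.00) | 16.20 → 13.67 (−2.53) |
| 50% | 2 | 18.70 → 16.35 (−2.35) | 18.36 → 15.41 (−2.95) |
| 60% | 1 | 15.41 → 12.52 (−2.89) | 15.21 → 12.18 (−3.03) |
| 60% | 2 | 17.91 → 14.29 (−3.62) | 17.81 → 14.02 (−3.79) |

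At 50%, the share of stopping trials that have already enrolled all 20 falls from 23% to 11% (1 per month) and from 54% to 21% (2 per month). With a 2-month lag the saving over all trials at 50% is about 1.6 to 2.1. At a 30% rate with a 3.5-month lag it is about 0.3, because few such trials stop.

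**The case against.** Several points on the other side stand.

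- **The lag is inferred.** A reader might infer that the rule waits for complete 3-month data. It does not say so: the 3 months belong to the gastrointestinal primary endpoint and the acute analysis, while the rule counts any related grade 3+ event. Appendix I also schedules an adverse event evaluation at 4-6 weeks. A shorter lag gives a smaller overrun. Conversely, Appendix I has a 4-month visit with a 30-day tolerance where the follow-up text in Section IV has 3 months, so the lag could be longer; those passages need reconciling.
- **A pause may be intended.** Continuing accrual if a boundary is not crossed could mean that accrual waits for the look. At 1 to 2 per month, 20 patients take 10 to 20 months; two 3.5-month pauses make that 17 to 27, a range that contains 24. This does not show that a pause is planned, but with one the overrun disappears.
- **The look at 15 is not idle.** A reader might infer that it does nothing. Without it, the chance of crossing at 50% falls from 79.4% to 76.1%. What it largely loses is the power to limit enrolment.
- **The saving depends on the true rate.** It is small where the regimen is tolerable. The background cites no grade 3 or higher toxicity in a 70-patient study of 6.6 Gy x 5, and 4 of 15 with grade 3 in a proton series. Enrolled is also not the same as treated, since enrolment precedes SBRT.
- **These are labelled feasibility rules.** The plan has a separate safety section and permits more frequent monitoring as needed. Neither sets a numeric running trigger for non-fatal events.
- **Early action is not free.** Attribution or evaluability may be revised, and a trial stopped sooner has fewer patients for the toxicity interval and for the completion rule, which is set on 20 evaluable patients.

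These points limit the size of the problem. They do not remove the gap in the text.

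**Conclusion.** The concern holds as an improvement to how the rule is applied. The boundaries are not in error, and the operating characteristics are the same either way. Without a pause, about 18 to 20 patients are enrolled when the look at 15 is complete if the lag is 3.5 months and accrual is 1 to 2 per month (about 17 to 18 at the 24-month pace), or about 17 to 19 if the lag is 2 months. At a true 50% rate a running count lowers mean enrolment by 2.0 to 2.4 patients over all trials with the longer lag; the larger figure of 2.5 to 3 applies only to trials that stop. These savings rest on the assumed lag, uniform event times and no pause. The documents do not support reading the look at 15 as worthless, or the change as wholly without cost. The change is worth making because it is cheap and matters most when the regimen is toxic.

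**What to change.** Keep the boundaries and the sample size. Add one sentence to Toxicity Stopping Rules: a boundary is crossed as soon as the count is reached and attribution and evaluability are confirmed, namely the 6th affected patient among the first 10 evaluable, the 7th among the first 15, or the 9th among the 20. State that the counts belong to those groups and that 6 or 7 events overall do not trigger a stop.

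In the same section, define when toxicity data are available, with the observation window and its starting point, and say whether accrual pauses at each look.

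The cost is a running count updated with each qualifying event, prompt confirmation of attribution and evaluability, and wider intervals for toxicity and completion if the trial stops earlier.

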--------------------	--

EXCLUSION CRITERIA	
 • Presence of metastatic disease. • Infections requiring systemic antibiotic treatment. • Unable to understand or unwilling to sign a written informed consent document. •
PROCEDURES	Endoscopically guided fiducial placement with optional biopsies obtained at the time of fiducial placement.
STATISTICAL CONSIDERATIONS	See statistics section.

SCHEMA

Eligibility: resectable or borderline resectable adenocarcinoma of the pancreas. Definition of resectable: no metastases, less than 180 degree involvement of hepatic artery, superior mesenteric artery or celiac artery

I. OBJECTIVES

Primary Objective

- To evaluate rates of acute (within 3 months of treatment) grade 3 or greater gastrointestinal toxicity.

Secondary Objectives

- To evaluate rates of late (> 3 months after treatment) grade 2 gastritis, enteritis, fistula, and ulcer, or any other grade 3 or greater gastrointestinal toxicity
- To determine rates of local progression free survival, overall survival, and metastasis- free survival in patients with resectable and/or borderline resectable pancreatic adenocarcinoma of the head and/or body undergoing neoadjuvant SBRT
- To evaluate patient quality of life before and after Linac based SBRT.
- To evaluate the margin positivity rate and pathologic complete response rate after Linac based SBRT.
- To further develop standardization of Linac based SBRT delivery and dosimetric parameters.

II. BACKGROUND

Natural History and Management of Pancreatic Cancer

More than 40,000 individuals are diagnosed with pancreatic cancer annually in the United States. Despite aggressive combined modality treatment approaches, five-year survival of patients with pancreatic cancer is still less than 5% (1). Clearly, more innovative treatments are needed to improve survival in this group of patients.

Surgical resection is considered to be the only potentially curative treatment option (2). However, the majority of pancreatic cancer patients do not have resectable and/or borderline resectable disease at presentation. More than 85% of patients have locally advanced or metastatic disease when initially diagnosed.

Current Adjuvant Management of Resectable and/or borderline resectable Pancreatic Adenocarcinoma

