Based upon prior phase I and phase II studies evaluating the toxicities associated with Linac based SBRT for pancreatic cancer, we estimate that $\leq 20\%$ of patients will experience grade 2 or higher late GI toxicity within one year. Late GI toxicities are those events occurring more than 3 months after Linac based SBRT. Acute GI toxicities are those events occurring within 3 months following Linac based SBRT. The major toxicity in this group of patients is the development of duodenal/gastric ulcers. Most of these are successfully managed medically. However, Stanford has observed 2 cases of duodenal perforation associated with Linac based SBRT in patients who did not undergo surgical resection of their tumors. We anticipate that because of refinements in radiation treatment planning techniques and because the dose will be divided over five treatments (as opposed to one), the biological equivalent and actual dose to the duodenum will be less than prior studies. Furthermore, the Stanford observed perforations occurred in duodenal locations that are routinely removed with pancreaticoduodenectomy, and all of our patients are anticipated to go to surgery. We anticipate that the risk of ulcer formation should be low ($< 5\%$) in this study. Hepatic and renal toxicity is not anticipated given the expectation of limited incidental irradiation of these organs.

Reporting of Serious or Unexpected Adverse Events

All fatal events, both anticipated and unanticipated, must be reported to the UC IRB within a time period as specified by current institutional guidelines after the PI learns of the event, whether or

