positive for asTF was significantly higher compared to that in all other cohorts ($p<0.01$, Chi-Square test). The mean asTF concentrations in the cohorts were as follows: PDAC, 0.403 ± 0.912 ng/mL; healthy subjects, 0.169 ± 0.596 ng/mL; the differences between mean asTF levels in the cohorts did not reach significance. Next, we evaluated asTF's potential as a biomarker to help detect a more aggressive PDAC phenotype. Among the 43 patients with PDAC, 36 were initially deemed resectable and 7 unresectable due to the presence of metastatic disease as determined by diagnostic screening; following exploratory laparoscopic surgery, 11 out of 36 patients initially deemed resectable were deemed unresectable due to the presence of metastatic disease. When the entire PDAC cohort was split into bona fide resectable (25) and unresectable (18) sub-cohorts, positivity for asTF was significantly more prevalent in the unresectable sub-cohort irrespective of the results of initial evaluation and/or pre-operative CA19-9 levels (asTF ≥0.2 ng/mL: 13 unresectable and 7 resectable patients; asTF <0.2 ng/mL: 5 unresectable and 18 resectable patients, $p=0.0059$, Fisher's exact test).

Our findings suggest that asTF at levels ≥0.2 ng/mL occurs more frequently in the plasma of patients with PDAC compared to healthy subjects. Further, PDAC patients whose plasma asTF levels were equal to or exceeded 0.2 ng/mL had a significantly lower chance to qualify for tumor resection, irrespective of initial pre-surgical diagnostic evaluation. asTF may thus comprise a novel marker of aggressive PDAC phenotype with potential utility in patient stratification, warranting prospective evaluation of larger PDAC patient cohorts.

Proposed research: prospective evaluation of asTF levels in circulation of patient with PDAC at 3 time points pre / post-SBRT (time point 0-14 days before surgery) and post-operative. Blood will be drawn in 3 ml sodium citrate tubes, ~1.5 ml of platelet poor plasma isolated, frozen until use, and assayed for asTF using ELISA as described above. We hypothesize that asTF levels will i) drop post-SBRT, ii) further drop post-resection, and iii) rise either concomitantly or shortly before recurrence. We also hypothesize that higher asTF levels at the onset and/or during the study will positively correlate with more aggressive disease and, consequently, poorer response to treatment.

XII. MEASUREMENT OF EFFECT

Anti-tumor Effect

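### The go and no-go halves of the completion-of-therapy rule count different things: only the go half requires an R0 or R1 resection, so some results meet neither half and the stated 80% does not hold for the no-go half

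*Combined protocol and SAP*

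**What the plan says.** The rule is in section IX, Completion of Therapy Stopping Rules, and has two bullets.

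- **Go:** "If at least 6 patients among 20 evaluable patients complete all preoperative and operative therapy including R0 or R1 resection", the study is taken to warrant phase II, provided that no other feasibility rule has been crossed.
- **No-go:** "If 5 or less than 5 patients among 20 evaluable patients complete all preoperative and operative therapy we will conclude" that feasibility has not been shown.

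A note under the no-go bullet gives the operating characteristics in terms of the R0/R1 resection rate: more than 80% chance of no-go at a rate of 20% or lower, and less than 13% at 40% or higher.

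Two other parts of section IX matter here.

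- Study Design and Decision Rules says that if no stopping rule has been crossed at the end of the trial, the regimen and design warrant phase II study.
- Supplementary Analysis Plans defines R0, R1 and R2 separately, with R2 meaning a macroscopically positive margin. The plan therefore foresees that a patient may be operated on and end with R2.

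**The concern.** The two bullets should be complements: every possible result among 20 evaluable patients should fall under exactly one of them. They are not, because the go bullet counts R0/R1 resections and the no-go bullet counts completed therapy of any margin status. A patient with an R2 resection can be left out of the first count and included in the second.

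A result can then fail the go criterion without triggering the no-go criterion. The plan's general default (no stopping rule crossed, so proceed) resolves that gap in favour of phase II. The number that stops the trial is then the looser count, while the quoted error rates were calculated for the stricter one. Completion of therapy is one of the three considerations on which section IX rests the feasibility decision.

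**Working it through.** **Inputs.** From section IX: n = 20 evaluable patients; go at 6 or more; no-go at 5 or fewer; reference R0/R1 rates 20% and 40%. Assumed, because the documents give no figure: an R2 rate of 1% or 5% of evaluable patients, with R2 patients counted as having completed operative therapy.

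**Step 1. Reproduce the stated figures.** Let X be the number with R0/R1 resection, X ~ Binomial(20, p).

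- P(X ≤ 5 | p = 0.20) = 0.804, stated as more than 80%.
- P(X ≤ 5 | p = 0.40) = 0.126, stated as less than 13%.

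Both agree. The figures belong to a rule that counts R0/R1 resections on both sides.

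**Step 2. Show the gap.** Let Y be the number with R2 resection. The go bullet needs X ≥ 6. The no-go bullet as worded needs X + Y ≤ 5. Results with X ≤ 5 and X + Y ≥ 6 meet neither. The simplest case is X = 5, Y = 1:

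| Count | Value | Bullet met? |
|---|---|---|
| R0/R1 resections | 5 of 20 (25%) | Go needs 6: not met |
| Completed operative therapy | 6 of 20 (30%) | No-go needs 5 or fewer: not met |

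No stopping rule is crossed, so the general rule declares that phase II is warranted.

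**Step 3. Error rate of the no-go bullet as worded.** X + Y ~ Binomial(20, p + q), where q is the R2 rate. With p = 0.20:

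| R2 rate q | p + q | P(X + Y ≤ 5) | Loss against 80.4% |
|---|---|---|---|
| 0% | 0.20 | 0.804 | none |
| 1% | 0.21 | 0.770 | 80.4 − 77.0 = 3.4 points |
| 5% | 0.25 | 0.617 | 80.4 − 61.7 = 18.7 points |

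The loss in the last column is also the probability of landing in the gap, since the gap is exactly the set of results with X ≤ 5 but X + Y ≥ 6.

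**Step 4. The other side.** At p = 0.40, counting R2 as completion can only lower the chance of no-go, so the stated limit of less than 13% still holds. Only the protection at 20% is lost. It had almost no slack to begin with (0.804 against 0.80).

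**The case against.** The strongest reply is that the intent can be recovered. The note under the no-go bullet describes the rule by the R0/R1 resection rate, so a careful reader would apply that endpoint to both bullets. The gap also needs at least one R2 resection near the boundary, and the plan's reporting of point estimates and confidence intervals would let phase II planners see the result. All of this is fair, and it makes the defect one of wording. It does not remove the defect: the text that triggers the decision lacks the condition, and the general default decides the unclear case towards phase II.

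A reader might infer something stronger: that 6 of 20 (30%) is too low a bar. Section VIII says "all of our patients are anticipated to go to surgery", and section XI reports that "11 out of 36 patients initially deemed resectable were deemed unresectable due to the presence of metastatic disease", which leaves 25 of 36 (69%). The documents do not carry that reading.

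- The section VIII statement is part of an argument about duodenal perforation, and going to surgery is not the same as R0/R1 resection. Section II expects some patients to progress before surgery.
- The 25 of 36 come from a biomarker cohort in which patients were reclassified because metastases were found at exploration. It is not an R0/R1 completion rate after chemotherapy and SBRT.
- Section III points the other way. In the multi-institutional series with the same fractionation, 17 of 70 (24%) had been resected so far, although that series includes locally advanced disease and was still maturing.

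Nor is this rule the only safeguard on the way to surgery, since toxicity, treatment-delay and treatment-related-death rules also apply.

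**Conclusion.** The completion rule is internally inconsistent as written. Its two bullets count different things, results such as five R0/R1 plus one R2 fall under neither, and the default then favours phase II. At an R0/R1 rate of 20%, the chance of no-go falls from 80.4% to 77.0% with 1% R2 and to 61.7% with 5% R2, below the stated 80% in both cases. This rests on two assumptions: that an R2 resection counts as completed operative therapy, which the no-go wording allows but does not state, and that R2 rates lie in the illustrated range. If no R2 resection occurs, the bullets agree and the stated figures hold.

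The arithmetic behind the stated 80% and 13% is correct. The 20% and 40% benchmarks have no stated source and look low beside the section VIII expectation about surgery, but whether they are too low is a judgement. A higher cut-off is not derivable from the documents and would have its own cost: a threshold of 11 of 20, for example, would give no-go 59% of the time at a true rate of 50%.

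**What to change.** In the no-go bullet, after "If 5 or less than 5 patients among 20 evaluable patients complete all preoperative and operative therapy", add the condition already in the go bullet, that completion includes an R0 or R1 resection. Six or more and five or fewer then split all results among 20 evaluable patients without a gap, and both bullets match the stated 80% and 13%.

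The cost is one phrase in a protocol amendment. The sample size, threshold and error rates stay as they are. The change should be made before the completion result is assessed.

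Optionally, the sponsor could add a sentence saying where the 20% and 40% rates come from, or tie them to a stated expected resection rate for resectable and borderline resectable patients after chemotherapy and SBRT. If that led to other rates, the threshold would have to be recalculated.
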